11	For Handyhaler or similar, check powder drug rests in capsule, if necessary, inhale again	Breathed out and away from the mouthpiece of the inhaler

Each subject in both intervention and control arm will receive standard assessment and instruction on inhalation technique according to criteria in Table 2 at baseline visit. The study endpoints will be collected at the follow-up visit (6-12 weeks).

Randomisation and masking

Each of the 80 subjects is stratified to block of 4 numbers according daily used inhaler of (1) DPI, (2) MDI or (3) both MDI/DPI. Simple randomisation (1 to 1) will be applied in each block and at each study site. The randomisation will be blinded for the evaluator at 6-12 week visit, which practically means that not the same study personnel will do the baseline randomisation and the final 6-12 weeks assessment of inhalation technique.

Endpoints

Primary endpoint is number of subjects presenting successful inhalation techniques as defined by objective endpoints divided by:

- DPI: PIF \geq 30 L/Min, time to PIF <0.5 seconds measured with the investigational device.
- MDI: inspiration time (> 3 seconds) and PIF less than 60 L/Min measured with the investigational device.
- Together with subjective critical endpoints at 6–12-week follow-up visit, assessed by study personnel, Table 2.

Secondary endpoints:

- Feasibility and safety of using the investigational device for education and training of inhalation technique based on questionnaire and interviews from subjects and healthcare personnel, Appendix 3.

Study personnel will get access and be trained in methods and procedures for informed consent, randomisation, investigational device, data collection and documentation. The study endpoints will be documented in electronic Case Report Form (CRF) provided by Karolinska Institutet. Data analysis will start as soon as all 80 included subjects have completed or considered to be lost to follow-up at 6-12 week's visit by local investigator.

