This RCT with multiple investigational sites consists of both primary and secondary level of asthma and COPD care to enabling generalizability of the results and implementation of the investigational device in different healthcare settings. Each study site has one local PI who is responsible for implementing and carry through the investigation. The local study team consist of experienced medical doctors and respiratory nurses in the field, who will receive support, training, and coordination in study procedures from the [name]'s research group at KI. The KI research group will ensure the implementation and progress of the study follow the time plan, but also transparency, streamline the collaboration and find local solution that can prevent occurrence of problems. The study sites will be monitored by Karolinska Trial Alliance (KTA) to ensure compliance with study protocol, safety rules and securing the integrity of subjects. KTA will also train and educate study personnel in Good Clinical Practice (GCP).

Completion of study will be done after subjects have completed the 6-12 weeks follow-up visit, but not later than 12 weeks. Subjects who do not attend the follow-up visit within specified timepoint will be lost to follow-up, not replaced and withdrawn from the primary analysis. Information about feasibility and safety (secondary endpoints) will be collected by healthcare personnel at the

investigational sites after 12 weeks if the study subject has used the investigational device. The investigational device will be removed from the AsthmaTuner app after study completion by [name] research group at Karolinska Institutet. The stratified block randomisation 1:1 between intervention and control arm per study site will ensure the reliability and validity of study results by eliminating selection bias, balance confounding variables.

A.6.2 Investigational device and comparator

Investigational device:

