Informed consent	X	
Randomization	X	
Questionnaires of medical history and usability	X	X
Spirometry test	X	
Standard review and correction of inhalation technique	X	X
Objective assessment of inhalation technique		X
Adverse events or device deficiency		X

Randomisation

Computer-based randomisation stratified for subjects' daily inhaler use into three groups of DPI, MDI or both DPI and MDI devices of four block numbers in each stratum per investigational site.

Interview and electronic questionnaires

- A structured health questionnaire completed at the first visit will provide information regarding medical history, health care utilization and experiences of inhalation education and training, Appendix 4.

Dynamic spirometry

- The lung function test will measure forced expiratory flow in one second (FEV₁), forced vital capacity (FVC), and FEV₁/FVC according standardised procedures [31]. Applied percent of predicted reference values, adjusting for age, sex, height, weight and ethnicity, will be calculated based on continuous prediction equations of normal population [32].

Standard review of inhalation technique

- All subject's ability to handle their inhaler(s) and inhalation technique will be reviewed and corrected at baseline visit and assessed at 6–12-week follow-up visit according to endpoints in Table 2.

Investigational device - app-based intervention for education and training of inhalation technique

1. Subjects randomised to intervention will receive instructions on using the investigational device, accompanied with written information (instructions for use) from study personnel at baseline visit. The subjects are instructed to use the investigational device 3-7 times per week to achieve the maximal effect.

2. Instruction for use manual on how to use medical investigational device will be available for subjects and study personnel at investigational sites (Appendix 5). Briefly, subjects follow the following procedure:
 - a. Baseline visit: Download (Apple Store or Google Play) and login with BankID or similar to the AsthmaTuner app. Automatic Bluetooth connection will be established between the MIR AsthmaTuner and the app.
 - b. Study personnel at Karolinska institutet set up login through BankID or SITHS card to AsthmaTuner Careportal for study personnel at investigational site.
 - c. Enter patient information: Fill out patient's initial letters, study ID, height, weight and type of inhaler. Press "next" to start the test.

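### A.6.1 makes collection of feasibility data depend on the device having been used, while the endpoint definition and Table 3 set no such condition, so app-arm non-users may go unrecorded

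*Protocol*

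**What the plan says.** The paragraph on study completion in A.6.1 contains one sentence on how the secondary endpoints are gathered. It begins "Information about feasibility and safety (secondary endpoints) will be collected by healthcare personnel at the" and ends "investigational sites after 12 weeks if the study subject has used the investigational device". The sentence before it deals with missed visits: "Subjects who do not attend the follow-up visit within specified timepoint will be lost to follow-up, not replaced and withdrawn from the primary analysis".

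Three other places describe the same data without a condition of use:

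- The endpoint list in A.6.1 defines the secondary endpoint as "Feasibility and safety of using the investigational device for education and training of inhalation technique", "based on questionnaire and interviews from subjects and healthcare personnel".
- The text below Table 2 in A.6.1 puts collection of the study endpoints at the 6-12 week follow-up visit.
- Table 3 in A.6.4 has a row "Questionnaires of medical history and usability", marked at baseline and follow-up, and a row "Adverse events or device deficiency", marked at follow-up.

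A.7 summarises feasibility and experienced benefit on a 1-5 Likert scale by mean and median. It does not say whose scores enter.

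**The concern.** Use of the app happens after randomisation and is part of what feasibility means. A subject who could not log in, could not pair the spirometer, or lost interest is direct evidence on the secondary aim of whether the device is feasible and usable. A rule that asks for feasibility information when the device has been used passes over that evidence. The Likert scores would then describe those for whom the device worked well enough to be used, which is a different and probably more favourable question.

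This is a data collection rule. A statistical analysis plan can choose an analysis set, but it cannot restore answers that nobody asked for. The stake is limited to a descriptive secondary endpoint; the primary analysis is not affected.

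**Working it through.** The plan gives no figure on this point, so the check sets the passages side by side and then illustrates direction and size under stated assumptions.

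**Step 1: who and when.**

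| Place | Who gives data | When |
|---|---|---|
| A.6.1, study completion | Subjects who have used the device | After 12 weeks |
| A.6.1, endpoint list | Subjects and healthcare personnel | Not stated |
| A.6.1, below Table 2 | No restriction | 6-12 week visit |
| A.6.4, Table 3, usability row | No restriction | Baseline and 6-12 week visit |
| A.6.4, Table 3, adverse event row | No restriction | 6-12 week visit |

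The first row disagrees with the others on both counts. The same A.6.1 paragraph also ends the study no later than week 12, so collection after 12 weeks falls outside the visit window.

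**Step 2: what counts as use.** No definition is given. The protocol describes intended use as daily (synopsis), at least weekly (A.6.1) and 3-7 times a week (A.6.4). The per-protocol set in A.7 takes more than one test a week on average. None of these is tied to the collection rule, and they need reconciling. Both arms also perform the objective test with the device at follow-up (A.6.4), so read literally even a control subject has then used it.

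**Step 3: who is lost under each reading.**

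- Broad reading (all subjects): every app-arm subject who never used the device.
- Narrow reading (only subjects who missed the visit, as the preceding sentence suggests): non-users who also missed the visit. Table 3 cannot recover them because they did not attend. If the 20% dropout in A.7 falls equally on the arms, this is at most 0.20 x 40 = 8 app-arm subjects, and only if none of them used the device.

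**Step 4: size, by illustration.** Input from the plan: 80 subjects allocated 1:1, so 80 / 2 = 40 in the app arm. Assumptions: those who answer have a mean score of 4.0; a share u of the arm is omitted; those omitted would have scored m.

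Whole-arm mean = 4.0 x (1 - u) + m x u

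Excess of the reported mean = u x (4.0 - m)

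For u = 0.20 and m = 2, the whole-arm mean is 4.0 x 0.80 + 2 x 0.20 = 3.6, and the excess is 0.20 x 2.0 = 0.40.

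| Share omitted (number of 40) | m = 1 | m = 2 | m = 3 | m = 4 |
|---|---|---|---|---|
| 5% (2) | 0.15 | 0.10 | 0.05 | 0 |
| 10% (4) | 0.30 | 0.20 | 0.10 | 0 |
| 20% (8) | 0.60 | 0.40 | 0.20 | 0 |
| 30% (12) | 0.90 | 0.60 | 0.30 | 0 |

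The excess is zero if nobody is omitted or if non-users would score the same as users. The shift in the median cannot be given without a distribution of scores.

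**The case against.** The sentence does not contain the word only. It follows directly on the sentence about missed visits and concerns the time after the window has closed, so it may describe extra collection from subjects lost to follow-up. It would then add data. Every attender, user or not, would remain covered by Table 3. This reading is fair, and it means a users-only rule for the whole trial cannot be taken as established. It does not clear the sentence, because non-users among those lost to follow-up are still passed over, and they may well include people who found the device unworkable.

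Complete non-users may also be few. Download, login and pairing are baseline steps in A.6.4, and lack of BankID or a smartphone is an exclusion. That limits the likely size. It does not remove the problem, since A.6.2 allows the equipment to be posted home and A.6.3 allows invitation by phone or digital meeting.

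Some evidence on non-use is held elsewhere. A.11 records downloads and dates of use, and A.14 counts malfunction and use errors as device deficiencies. The proportion of non-users can therefore be obtained, but nothing in the protocol says that it will be reported, and the reasons for non-use are not covered.

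A reader might infer that safety data, too, would come from users alone, with no control comparison. The documents do not support this. Table 3 lists adverse events at follow-up without condition, A.6.5 monitors all adverse events whether device related or not, and A.14 covers events regardless of relation to the device and applies its causality considerations to the comparison group. Linking device-effect data to exposure is in any case usual.

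**Conclusion.** The point holds as an inconsistency in a collection rule that can favour the device. A.6.1 ties feasibility data to an undefined condition of use and a time after 12 weeks, while the endpoint definition and Table 3 do neither. If the condition is followed, app-arm non-users, or on the narrow reading those who also missed the visit, give no feasibility data, and later analysis cannot repair this.

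It is tempting to go further and call upward bias certain. The documents do not allow that: the direction is likely because non-users would probably rate the device lower, but this is an assumption, and no non-use rate or score is given. In the illustration the excess runs from 0 to 0.90 Likert points, depending entirely on assumed values.

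**What to change.** Replace the A.6.1 sentence with wording to this effect: feasibility and usability are collected from every subject randomised to the app arm, including those who never used or stopped using it, together with reasons for non-use. Collection takes place at the 6-12 week visit or, for those lost to follow-up, through the email, phone or letter contact already planned in A.6.3. Align the timing with the text below Table 2 and with Table 3.

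Define use for reporting purposes from the dates of use recorded under A.11, leaving out the objective test that both arms perform at follow-up. Report the proportion of non-users as a feasibility result with the app arm as denominator. State that adverse events and device deficiencies are collected in both arms, as Table 3 and A.14 already imply.

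The cost is a short change of text and a brief questionnaire or contact for non-users. Dates of use are already kept and subjects lost to follow-up are already contacted, so little new work is needed.

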Procedures: At baseline, a trained respiratory nurse will subjectively assess and train each patient's inhalation technique according to defined criteria of device handling (standard education). The AsthmaTuner app is downloaded to a smartphone or tablet computer (Ipad) that is wirelessly (Bluetooth) connected to a home spirometer. In this study the Bluetooth spirometer AsthmaTuner from MIR will be used. Education and training of inhalation technique will include measurement of inhalation flow with an adjustable resistance mounted on the spirometer, Airflow Trainer (MIR). The app gives instruction to set the resistance, so it corresponds to the selected inhaler. Questionnaires and interviews will collect information about the feasibility, safety and experienced usability of the investigational device.

Analysis: The rate of subjects with successful inhalation technique at 6–12-week visit determined by fulfilling objective and subjective critical endpoints in intention-to-treat approach. The effect of using the inhalation app-module will be analysed with logistic regression analysis across randomisation groups. The secondary analysis of feasibility and the experienced benefit of using the inhalation app-module in clinical practice and for patient's education and training of inhalation technique is estimated on a Likert scale from 1 (not at all) to 5 (strongly agree) and presented as mean and median scores.

A.2 Identification and description of the investigational device

A.2.A Description of the investigational device

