A.6 Design of the clinical investigation

A.6.1 General

This confirmatory multicentre two-armed stratified randomised controlled blinded study analysing the effect of app-based education and training of inhalation technique compared with control group on subjective critical and objective endpoints of inhalation technique at 6-12 weeks follow-up visit. The study approach is intention to treat, including 80 subjects with daily therapy of DPI and/or MDI for asthma and/or COPD, Figure 2.

[figure not shown]

Figure 1 Two-armed, parallel-designed, individual single-blinded stratified randomised controlled trial.

The subjects will be randomly assigned to one of the following two arms (1:1):

1. Standard assessment and correction together with app-based education and training at baseline visit and at least every week or whenever needed during the following study period of 6-12 weeks.
2. Standard assessment and instructions on inhalation technique at baseline visit according to Table 2.

Table 2. Subjective assessment of handling and inhalation techniques, adopted from Aksu F. et al. [8]. If all criteria are not deemed to correction per inhaler, including objective endpoints defines primary endpoint of subject with successful inhalation technique.

	DPI	MDI
1	Shook inhaler (critical for Easyhaler)	Shook the inhaler (critical for suspension)
2	Removed the cap of the inhaler correctly (critical)	Removed the cap of the inhaler correctly (critical)
3	Actuated one dose / loaded capsule correctly (critical)	Breathed out before slow inhalation
4	Inhaler kept in upright position (critical for some inhalers)	Breathed out and away from the mouthpiece of the inhaler
5	Breathed out and away from the mouthpiece of the inhaler	Placed the inhaler mouthpiece correctly in mouth
6	Inhaler correctly placed in mouth. Inhaled with lips sealed around the mouthpiece (critical)	Inhalation slow before or immediately when dose fired (critical)
7	Inhaled forcefully through the mouth after firing dose (critical)	Inhaled through the mouth after dose fired (critical)
8	Inhaled without interruption (critical)	Inhaler was correctly placed in mouth during the entire inhalation (critical)
9	Breath-holding more than 5 seconds after inhalation	Inhaled without interruption (critical)
10	Breathed out and away from the mouthpiece of the inhaler	Breath-holding more than 5 seconds after inhalation

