Subjects lost to follow-up will not be replaced but the decision will be documented in the medical record. Subjects who not attend the follow-up visit 12 weeks after the baseline visit will be categorised as lost to follow-up. They will be asked through email, phone or letter to send in the medical device to the study centre with envelope they received when they received the device at baseline visit. Study sites will be informed about which subjects were lost to follow-up.

Point of enrolment and randomisation

At least 80 subjects will be invited to participate in the investigation, through phone, digital meeting (Teams or Zoom or similar) or at physical at the baseline visit. The study personnel at investigational site will contact the study centre through phone to receive the randomisation assignment and study ID. The anticipated distribution is a minimum of 10 subjects per each participating investigational site.

Expected duration of each subject's participation is 6-12 weeks after enrolment to the investigation. The follow-up visit will be booked 6 weeks after study enrolment but no longer than 12 weeks. Subjects unable to attend the 6-12-week follow-up visit will be withdrawn from the primary analysis of study. The number of subjects required to be included in the investigation is estimated on background of power calculation (see section A7). The timeline is to enrol subject to the investigation during the fall of 2024 and spring of 2025. No additional care is required after the investigation beyond what was initially planned for each subject.

Target and vulnerable populations

The target population for the medical device are patient treated for asthma or COPD or any other disorder requiring treatment with DPI or MDI in primary or secondary care setting. However, neither patient with other diagnosis or children under the age of 16 years will not be included in the study. Although schoolchildren below the age of 16 are considered as target populations for the medical device, we consider we have sufficient data from this population from the pilot study (Appendix 4). Vulnerable, pregnant and breastfeeding population fulfilling the inclusion criteria are welcome to participate, no adverse effects or events are expected in this vulnerable population as longs they will be able to attend the follow-up visit.

A.6.4 Procedures

The subjects will undergo the following procedures as summarized in Table 3.

Procedures	Baseline visit	6–12-week follow-up visit

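### The protocol does not require the standard education given to both arms to be finished before the site learns the assignment, so teaching that differs by arm is possible

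*Protocol*

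**What the plan says.** - **Common component.** A.6.1, below Table 2: "Each subject in both intervention and control arm will receive standard assessment and instruction on inhalation technique according to criteria in Table 2 at baseline". In the synopsis (A.1.5) this task falls to a trained respiratory nurse. A.6.4 says that every subject is reviewed and corrected at baseline.
- **Assignment.** A.6.3: "The study personnel at investigational site will contact the study centre through phone to receive the randomisation assignment and study ID".
- **Schedule.** A.6.4 introduces the schedule with "The subjects will undergo the following procedures as summarized in Table 3". Under the baseline visit the rows run: consent, "Randomization", questionnaires, spirometry, "Standard review and correction of inhalation technique".
- **Masking.** A.6.1 masks the evaluator at the 6-12 week visit. It asks only that the staff who randomise at baseline are not those who make the final assessment.
- **The two arms.** A.6.1 describes arm 1 as "Standard assessment and correction together with app-based education and training at baseline visit". Arm 2 is described as standard assessment and instructions, with no mention of correction. A.6.2 lets sites use manual flow meters in the control group where these belong to local standard care.

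**The concern.** The trial claims that the app is superior to standard education (A.5), so education is what is being compared. The standard session is the control arm's entire study intervention, and arm 1 is meant to receive the same session plus the app. The app's effect is isolated only if that shared part really is the same in both arms.

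Correcting technique is interactive. Table 2 lists what to check, but sets no duration, number of repetitions or stopping point. Staff who know the arm could coach controls harder because they get nothing else, or app subjects more lightly because the app will follow. They could also favour the app arm. The bias could go either way. Because it would be a real difference in technique, masked assessment at follow-up would record it faithfully and not correct it.

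**Working it through.** No arithmetic settles this point. The question is whether any text, alone or combined with others, keeps the arm unknown until the shared education is complete.

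1. **Explicit order rules.** The only one is in A.15: signed consent comes before randomisation. No sentence places the Table 2 review before or after the assignment.
2. **Table 3.** Randomisation is the second row and the standard review and correction the fifth. Both are marked in the same baseline column and the table is called a summary. It does not fix a sequence within the visit, but a site working from top to bottom complies and teaches after allocation.
3. **Who learns the arm, and when.** Site personnel do, by phone (A.6.3). Assignment and study ID arrive in the same call. The electronic CRF takes direct entry (A.8) and identifies subjects by code, which gives a practical reason to phone early.
4. **Who is masked.** Only the follow-up evaluator (A.6.1). A.16 says that allocation must not be disclosed to physicians and investigators, but it names the study nurse as a source if unblinding is needed. That implies that the nurse knows the arm at some point. It does not say when.
5. **Is the shared component defined identically?** The text following Table 2 in A.6.1, and A.6.4, treat both arms alike. The arm descriptions in A.6.1 do not: arm 1 has correction, arm 2 has instructions. The meter clause in A.6.2 is written for the control group, and staff can apply a control-only permission at the baseline session only if they know the arm.
6. **Link to the primary endpoint.** Success requires the critical Table 2 steps together with the objective flow criteria (A.6.1, A.7). The Table 2 steps are what the standard session teaches. PIF, the one quantity that A.6.2 says the meter measures, is among the objective criteria.
7. **Is early allocation needed?** Stratification uses site and inhaler type (DPI, MDI or both). Both are known before any teaching, so nothing in the randomisation scheme requires the call to come first.

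Steps 1 to 4 show that the order is open and the educator unmasked. Step 5 shows two places where the text itself separates the arms. Step 6 shows the route to the endpoint.

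**The case against.** The strongest reply is that three tempting readings go beyond the text.

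- **A reader might infer that Table 3 orders randomisation before education.** It does not. It summarises by visit, and the synopsis opens its account of procedures with the nurse's assessment and training, before the app download.
- **A reader might infer that the teaching nurse necessarily knows the arm.** The documents do not say so. Study personnel phone for the assignment and a respiratory nurse teaches. Nothing says that they are the same person or that the nurse has been told by then.
- **A reader might put a figure on the lost power or the inflated effect.** Any such figure needs an assumed shift in success rates, for which the documents give no basis. Table 1 notes that errors often recur within 4-6 weeks of training, so a difference from one session may fade before follow-up.

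Three further points are fair. Both arms are taught to one checklist, which limits the scope for difference. Part of the endpoint is measured by instrument. No planned analysis uses a baseline Table 2 score, so arm-aware recording at baseline would do little harm to the stated analyses.

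These points narrow the concern but do not remove it. A shared checklist does not fix how hard each step is coached, an instrument records whatever technique was taught, and the protocol still contains no safeguard on order or masking of the educator. It is also true that staff who know the arm could coach further after the call, so reordering reduces the opportunity without closing it entirely.

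**Conclusion.** The concern holds as a gap in the design: the protocol leaves open whether the shared education is given before or after the assignment is known, and does not mask the person who gives it. The differing arm descriptions and the control-group meter clause make unequal delivery more plausible than row order alone would. The consequence is possible bias in either direction in the critical handling steps of the primary endpoint. Its size cannot be derived from the documents, and nothing in them shows that it will occur. The conclusion assumes only that coaching intensity can vary within the Table 2 checklist and that some of its effect can last to the follow-up visit. The change is worth making because it is cheap and the session at issue is the control arm's whole intervention.

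**What to change.** 1. In A.6.3 and Table 3, state the order of the baseline visit: consent, questionnaires, spirometry, and the Table 2 review and correction, all completed and recorded. Then phone for the assignment. Then set up the app, for the intervention arm only.
2. Because one call now delivers both ID and assignment, either issue the study ID separately at consent, or let baseline forms be coded straight after the call.
3. Reconcile the two arm descriptions in A.6.1 with each other and with A.6.4, and reconcile the meter clause in A.6.2, so that the standard component is the same in both arms at any given site.

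The cost is a reordering within one visit plus a separate ID step or a short delay in coded entry. No extra visit is needed.
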